8.2.3.3.1 Hematological parameters

For the whole treatment period, the worst value of each hematological parameter will be calculated for each patient. The worst value of each parameter will then be coded and the frequency of each category will be tabulated. A table with grade 3 or 4 rates will be provided.

8.2.3.3.2 Biochemical parameters

For the whole treatment period, the worst value of each biochemical parameter will be calculated for each patient. The worst value of each parameter will then be coded and the frequency of each category will be tabulated. A table with grade 3 or 4 rates will be provided.

8.2.3.3.3 All AEs

The worst grade of each AE item will be calculated as the maximum grade reported **regardless of seriousness or relationship** for that item over the whole treatment period. The frequency of the worst grade of each AE item will be tabulated. A table with grade 3 or 4 rates will be provided.

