1.1.4 Further considerations for anaplastic glioma

Neither the role of adjuvant chemotherapy after radiotherapy nor the role of concurrent chemo-irradiation has been established in anaplastic glioma. Various surveys among clinicians underline the absence of evidence based consensus on how to treat these patients: different institutions have adopted various strategies, including radiotherapy only, radiotherapy followed by adjuvant chemotherapy (with a variety of regimens), and concurrent chemo-irradiation with or without further adjuvant treatment.

Moreover, if indeed adjuvant treatment does not increase overall survival in this patient population (as suggested by both EORTC 26951 and RTOG 9402), postponing chemotherapeutic treatment until recurrence will avoid the continuation of an inactive treatment in unresponsive patients. This would shorten initial treatment considerably, and would be an argument to stop treatment at the end of irradiation and to withhold further treatment until progression. On the other hand, postponing progression by adjuvant treatment may help to keep patients in a better condition.

Because of significant toxicity of the PCV regimen in EORTC 26951 and RTOG 9402 studies (Ref. 9, Ref. 10) and good tolerability of temozolomide overall and in the EORTC 26981 study (Ref. 11), temozolomide serves as preferred drug for future trials of radiochemotherapy.

These considerations and the concern for late toxicities require a prospective trial to examine the role of adjuvant and concurrent temozolomide chemotherapy in non-1p/19q co-deleted anaplastic glioma.

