5.2.1.10 Potential Late Complications

Depending on the tumor location and the region to be irradiated, several tissues or organs are potentially at risk for late damage, such as cortical brain, brain stem, chiasm, ear (mid or internal) and pituitary gland. All efforts should be made during planning to minimize the dose to critical structures. Late complications will be recorded according to CTC version 3.0

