6.4.1 Six monthly disease evaluation after the end of radiotherapy

All patients would have six monthly disease and status assessment after the end of radiotherapy.

- Physical examination including neurological evaluation
- Corticosteroid intake
- MMSE
- Quality of Life C30 and BCM20
- WHO-ECOG performance status
- Toxicity according to CTCAE v.3
- Gd-enhanced MRI or contrast CT scan of the brain
- Cognitive exam; dedicated centers only, to be carried out yearly after the start of radiotherapy (e.g., 12 months, 24 months, 36 months etc)

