8.2.3.3 Analyses methods for safety endpoints

The safety analyses will be presented overall and by period as defined below:

- The baseline (BL) period will include all information recorded up to the randomization date.
- The radiation therapy (RT) or chemo/radiation period (RT&TMZ) will start on the day the radiation therapy is first given and end the day of the last administration of radiation therapy treatment plus 28 days.
- The adjuvant chemotherapy period (RT+TMZ) will start 29 days after the last dose of radiation therapy treatment and end-up 27 days after the first day of administration of the last cycle of adjuvant chemotherapy.
- The follow-up period (FUP) will start 29 days after the last dose of radiation therapy treatment or 28 days after the first day of administration of the last cycle of adjuvant chemotherapy.

The safety assessments include hematological toxicity, laboratory measurements and adverse events. Only the safety assessments performed before progression or within 7 days of progression and before start of any further anti-cancer therapy will be included in the analysis.

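### The adverse-event tables use an undefined treatment period that is not reconciled with the planned follow-up period, and a crude worst grade would not compare late toxicity like for like

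*Combined protocol and SAP*

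**What the plan says.** Section 8.2.3.3 opens with a general rule: "The safety analyses will be presented overall and by period as defined below". It then lists baseline, radiotherapy (with or without temozolomide), adjuvant and follow-up periods. The radiotherapy period is to "end the day of the last administration of radiation therapy treatment plus 28 days". The adjuvant period closes 27 days after day 1 of the last cycle. For the last period, "The follow-up period (FUP) will start 29 days after the last dose of radiation therapy treatment or 28 days after the first day of administration" (meaning the final adjuvant cycle); no end is given. Only assessments up to 7 days after progression, and before any further anti-cancer therapy, are used.

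The two adverse-event tables follow. In 8.2.3.3.3 (all events) and 8.2.3.3.4 (likely related events) the worst grade is taken "for that item over the whole treatment period. The frequency of the worst grade of each AE item will be tabulated". Neither section mentions follow-up, and the term for the window is not defined anywhere.

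On late toxicity, section 1.1.2 says it is unknown whether combined treatment increases delayed neurotoxicity in longer survivors. Section 1.1.4 gives as part of the rationale that "the concern for late toxicities require a prospective trial to examine the role of adjuvant and concurrent temozolomide chemotherapy". Section 5.2.1.10 names brain, brain stem, chiasm, ear and pituitary as at risk and says "Late complications will be recorded according to CTC version 3.0". Section 6.4.1 states that "All patients would have six monthly disease and status assessment after the end of radiotherapy", and CTCAE toxicity is on that visit list and in the 6.6 table.

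**The concern.** The general rule and the table definitions point to different windows. A programmer working from 8.2.3.3.3 and 8.2.3.3.4 could stop at the end of treatment; one working from 8.2.3.3 would add a follow-up table, but would have to invent its metric. The two would report different late toxicity from the same data.

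The second difficulty remains even if follow-up tables are produced. The follow-up window opens at the end of each patient's own treatment, so adjuvant temozolomide itself moves the window. A crude worst grade per window then sets different stretches of time after radiotherapy against each other. At stake is whether the report can say anything comparable about late non-cognitive toxicity, which the protocol gives as part of its reason for the trial.

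**Working it through.** The plan gives no figure on this point to reproduce. The check is a reading of the sections plus day arithmetic.

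**Inputs.** Radiotherapy lasts 6.5 weeks = 45.5 days (5.2.1). Adjuvant treatment is at most 12 cycles of 28 days (5.2.2.4). Period limits are from 8.2.3.3. Six-monthly visits are counted from the end of radiotherapy (6.4.1), with a month taken as 30.4375 days. Assumption: cycle 1 starts on day 29 after radiotherapy and no cycle is delayed.

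**Where the periods fall (days after last radiotherapy dose).**

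- Arms 1-2: the radiotherapy period ends on day 28 and follow-up opens on day 29.
- Arms 3-4: cycle 12 day 1 = 29 + 11 × 28 = 337. The adjuvant period ends on 337 + 27 = 364, and follow-up opens on 337 + 28 = 365.
- Gap in opening dates: 365 − 29 = 336 days, about 11 months.
- For k cycles, follow-up opens on day 29 + 28k, so the gap is 28k days: 28 days after 1 cycle, 168 after 6, 336 after 12. Early stopping shortens the gap; delays lengthen it.

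**Where the six-monthly toxicity grades fall.**

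| Visit after RT | Day | Arms 1-2 | Arms 3-4 (12 cycles) |
|---|---|---|---|
| 6 months | 183 | follow-up | adjuvant |
| 12 months | 365 | follow-up | first day of follow-up (borderline) |
| 18 months | 548 | follow-up | follow-up |
| 24 months | 730 | follow-up | follow-up |

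**Reading A: the tables cover radiotherapy and adjuvant periods only.** Measured from the start of radiotherapy, they close at (45.5 + 28) / 30.4375 = 2.4 months in arms 1-2 and at up to (45.5 + 364) / 30.4375 = 13.5 months in arms 3-4. Arms 1-2 contribute no six-monthly grade; arms 3-4 contribute the 6-month grade, with the 12-month grade borderline.

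**Reading B: the same tables are also made for follow-up.** Late grades are now shown, but arms 1-2 are observed from about month 1 after radiotherapy and arms 3-4 from about month 12. This affects mainly Question II (arms 1-2 against arms 3-4). For Question I (arms 1 and 3 against arms 2 and 4), each side mixes one early-opening and one late-opening arm, so the windows are roughly balanced.

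**Reading C: one overall worst grade.** The start is common to all arms, but a late event cannot be told from an acute one in the same item.

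None of the three gives a like-for-like description of late toxicity by arm.

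**The case against.** The strongest reply is that 8.2.3.3 governs its own subsections. It requires presentation by period and goes to the trouble of defining a follow-up period, which would serve no purpose if follow-up grades were never shown. An undefined phrase is an ambiguity, not proof of loss, and presentation by period does separate late from acute events. This stands. A reader might infer from 8.2.3.3.3 and 8.2.3.3.4 alone that follow-up toxicity enters no table; the documents do not support that.

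Nor do they support the inference that the plan ignores late neurological harm. Objective 2.2 names late effects on cognition specifically. These have the MMSE analysis (8.2.3.4) and a yearly side study at dedicated centers (Appendix I). The QLQ-BN20 includes visual disorders and motor dysfunction (10.2), and sustained loss of performance status is a separate endpoint (7.2). Likely related serious events stay reportable after day 30 (16.6). What these do not supply is CTCAE-graded late effects: hearing and pituitary function, for example, are in none of the descriptions.

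Two further extensions fail. The haematology and biochemistry tables use the same phrase, but those tests are not scheduled at the six-monthly visits, so little scheduled data is affected. And the share of patients alive when treatment ends does not measure lost late events, because 8.2.3.3 cuts safety data off around progression or at further therapy.

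Finally, the plan chose descriptive safety reporting without p-values (8.2.3.3.4). The remedy should respect that.

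**Conclusion.** The point holds in a limited form. The adverse-event table definitions are not reconciled with the period rule that introduces them, and no metric is stated for the follow-up period. If follow-up tables are made with the stated crude worst grade, the windows open about 336 days apart between arms 1-2 and arms 3-4, so late non-cognitive toxicity is not compared like for like, mainly for the adjuvant question.

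The 336 days assumes 12 undelayed cycles starting on day 29; it is 28 days per cycle given. No number of missed or misplaced events can be derived from the documents, and none is claimed. Primary and secondary efficacy analyses are untouched. This is a worthwhile improvement at low cost, not a demonstrated absence of follow-up safety reporting.

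**What to change.** 1. In 8.2.3.3.3 and 8.2.3.3.4, replace the treatment-period wording with *over each period defined in 8.2.3.3, including follow-up, and overall*.

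2. Add one descriptive analysis, without p-values: cumulative incidence from randomization of first grade ≥2 and first grade ≥3 neurological and other late radiation items (the organs in 5.2.1.10), by arm and by question, shown at 1, 2, 3 and 5 years. Treat progression and death as competing events. State how further anti-cancer therapy started before progression is handled, so that the analysis matches the cut-off in 8.2.3.3. List the items in advance, and say how an item already at that grade at baseline is counted, since 8.2.3.3.4 leaves baseline grades out of account.

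The common origin removes the unequal start of the follow-up windows; the by-period tables keep acute and late events apart.

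Cost: SAP wording and a few tables and curves from CTCAE grades already collected. No new visits or patients, and no clinical rule changes. The limits should be stated with the results. Late events will be sparse, and after treatment they are ascertained only six-monthly. Arms 3-4 are also graded before each adjuvant cycle (6.4.2.1), so first-year differences on the adjuvant question partly reflect closer observation.

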8.2.3.3.4 Related AEs

The worst grade of each AE item will be calculated as the maximum grade reported **as likely related** for that item over the whole treatment period. The frequency of the worst grade of each AE item will be tabulated. A table with grade 3 or 4 rates will be provided.

There will be no formal comparison of safety endpoints. No p-value will be carried out.

Baseline AE grades will not be accounted for in any AE analyses.

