7.5 Evaluation of toxicity

7.5.1 Adverse events and side effects

All adverse events will be recorded on the case report forms; the investigator will decide if those events are drug related (unrelated, likely related, not assessable) and his decision will be recorded on the forms for all adverse events.

Adverse events not drug related (i.e. reported as unrelated) will not be considered as side effects or toxicity.

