16.4 Causality assessment

The investigator is obligated to assess the relationship between protocol treatment and the occurrence of each SAE following definitions in this table:

Relationship to the protocol treatment	Description
UNRELATED	There is no evidence of any causal relationship to the protocol treatment
LIKELY RELATED	There is (some) evidence to suggest a causal relationship to the protocol treatment and influence of other factors is unlikely or absent.
NOT ASSESSABLE	There is insufficient or incomplete evidence to make a clinical judgment of the causal relationship to the protocol treatment.

The investigator will use clinical judgment to determine the relationship. Alternative causes, such as natural history of the underlying diseases, medical history, concurrent conditions concomitant therapy, other risk factors, and the temporal relationship of the event to the protocol treatment will be considered and investigated.

The decision will be recorded on the Serious Adverse Event form, if necessary with the reasoning of the principal investigator.

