16.6 Reporting procedure for investigators

This procedure applies to all Serious Adverse Events (SAE) occurring from the time a subject is randomization until 30 days after last protocol treatment and to any SAE that occurs outside of the SAE detection period (after the 30-days period), if it is considered to be likely related to the investigational product or study participation.

Randomization till 30 days after last protocol treatment:	All SAEs
From day 31 after last protocol treatment:	Only related SAEs

All reporting must be done by the principle investigator or authorized staff member (i.e. on the signature list) to confirm the accuracy of the report.

All SAE data must be collected on the study-specific SAE form.

All SAEs must be reported immediately and no later than 24 hours from the time the investigator or staff became aware of the event.

All SAE-related information needs to be provided in English.

All additional documents in local language must be accompanied by a translation in English, or the relevant information must be summarized in a follow-up SAE report form.

Investigators participating through **EORTC** must fax/e-mail all SAE-related information to:

EORTC Pharmacovigilance:

[contact]

E-mail: [contact]

Investigators participating through **non-EORTC groups** should consult their **group specific appendix** for further details on the reporting of Serious Adverse Events.

To enable the EORTC to comply with regulatory reporting requirements, all initial SAE reports should always include the following minimal information: an identifiable patient (SeqID), a suspect medicinal product if applicable, an identifiable reporting source, the description of the medical event and seriousness criteria, as well as the causality assessment by the investigator. Complete information requested on the SAE form of any reported serious adverse event must be returned within 7 calendar days of the initial report. If the completed form is not received within this deadline, the EORTC Pharmacovigilance will make a written request to the investigator.

Queries sent out by the EORTC Pharmacovigilance need to be answered within 7 calendar days.

All forms need to be dated and signed by the principle investigator or any authorized staff member (i.e. on the signature list).

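### The related-AE table leaves out events rated *not assessable*, which section 7.5.1 keeps as toxicity, so that table may understate related AEs

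*Combined protocol and SAP*

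**What the plan says.** Section 7.5.1 has the investigator decide, for every adverse event on the case report forms, whether it is "drug related (unrelated, likely related, not assessable"). It then sets the rule for what counts: "Adverse events not drug related (i.e. reported as unrelated) will not be considered as side effects or toxicity". No other rating is excluded.

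Section 8.2.3.3.4 (Related AEs) takes, for each AE item, the "maximum grade reported as likely related for that item over the whole treatment period", and tabulates worst grades and grade 3 or 4 rates. It does not say where events rated *not assessable* are shown by relationship.

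Section 16.4 defines the three ratings for SAEs. The bar for *likely related* has two parts: "There is (some) evidence to suggest a causal relationship to the protocol treatment and influence of other factors is unlikely or absent". The rating *unrelated* applies only where nothing at all points to treatment as a cause. The third rating, *not assessable*, is for events on which the information is too thin to judge; it does not mention competing causes.

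Section 16.6 extends SAE reporting beyond 30 days after last protocol treatment to an event "if it is considered to be likely related to the investigational product or study participation". The small table beneath that text says simply that related SAEs are reported from day 31.

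**The concern.** The protocol and its analysis section draw the line for treatment toxicity in different places. One keeps everything except *unrelated*; the other keeps only *likely related*. The middle rating falls between them.

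This matters because the related-AE table is the only planned AE table that tries to separate treatment effects from background. Section 8.2.3.3.4 also states that baseline grades are not taken into account in any AE analysis, so the all-AE table mixes pre-existing tumour symptoms with toxicity. A reader who wants attributed toxicity will turn to the related-AE table, and the narrower rule makes that table look more favourable than the protocol's own definition would.

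**Working it through.** There is no figure in the plan to reproduce. The check is a comparison of sections, followed by an illustration.

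**1. Which events each section counts**

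| Rating | Toxicity under 7.5.1 | Related-AE table (8.2.3.3.4) | All-AE table (8.2.3.3.3) |
|---|---|---|---|
| Likely related | yes | yes | yes |
| Not assessable | yes (not excluded) | no | yes |
| Unrelated | no | no | yes |

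The two definitions of toxicity differ in the middle row only.

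**2. Direction.** For one patient and one AE item, let *L* be the set of events rated likely related and *N* the set rated not assessable. The plan takes the maximum grade over *L*; the 7.5.1 rule implies the maximum over *L* and *N* together. A maximum over a subset cannot exceed the maximum over the whole set. So the number of patients with any related event, or with a related event of a given grade or worse, is at most the 7.5.1 count. Single-grade cells can move either way, because adding *N* may shift a patient from one grade to a higher one.

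**3. Size (illustration only).** Let *p* be the proportion of patients with an AE of a given item not rated unrelated, and *q* the share of those events rated not assessable. With one event per patient per item,

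tabulated related rate = *p* × (1 − *q*).

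The documents give neither input. Assuming *p* = 10%:

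| Assumed *q* | Tabulated related rate | Rate under 7.5.1 |
|---|---|---|
| 0% | 10% × 1.00 = 10% | 10% |
| 10% | 10% × 0.90 = 9% | 10% |
| 25% | 10% × 0.75 = 7.5% | 10% |
| 50% | 10% × 0.50 = 5% | 10% |

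If a patient has several events of the same item, one *likely related* event keeps that patient in the table, although the worst grade shown may be lower. The loss in patient counts can then be smaller than this formula gives.

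**4. Which events might be rated *not assessable*.** Take an event with some evidence for treatment and a plausible competing cause. It fails *unrelated*, because there is some evidence. It fails *likely related*, because other factors are neither unlikely nor absent. It does not plainly meet *not assessable* either, since that rating is defined by a lack of evidence. It therefore meets no definition expressly. Some such events may end up as *not assessable*, but that is an inference by elimination. It also needs the SAE definitions to carry over to all AEs: section 16.4 introduces them with "The investigator is obligated to assess the relationship between protocol treatment and the occurrence of each SAE following definitions in this table", while 7.5.1 uses the same labels without defining them.

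**5. Where the effect stops.** Section 8.2.3.3.3 counts every AE whatever its relationship. Sections 8.2.3.3.1 and 8.2.3.3.2 take worst laboratory values with no relationship filter. None of these tables changes with *q*.

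**6. Section 16.6.** The text uses *likely related* as the threshold from day 31 and the table uses *related*. If *related* carries the sense of 7.5.1, these are different thresholds within one section.

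**The case against.** The strongest reply is that nothing recorded is lost. Every *not assessable* event within the safety window is in the all-AE table with its grade. The toxicity endpoint in 8.2.1.4 is the frequency of AEs, not of related AEs. Section 5.5.3.1 expects most temozolomide toxicity to be haematological, and that is tabulated without attribution. Radiotherapy alone is a randomised arm, so all-cause rates by arm show excess toxicity without relying on investigator judgement. Late cognitive effects are compared formally through the MMSE (8.2.3.4). All of this stands, and it limits the point to one table.

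It also rules out three stronger readings that a reader might infer:

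- *Temozolomide toxicity is under-reported in this trial.* The unfiltered tables contradict this. Section 16.4 moreover rates relationship to protocol treatment, which includes radiotherapy, while 7.5.1 speaks of drug-related events. The related-AE table is thus not clearly a temozolomide-specific measure.
- *The scale forces events with a competing cause into *not assessable*.* Section 16.4 does not say so. It leaves the rating to clinical judgement after alternative causes have been considered.
- *Late serious events with mixed causes never reach the sponsor.* Section 16.6 governs the SAE form. All AEs go on the case report forms, and toxicity is assessed six-monthly before progression (6.4.1). The schedule after first progression (6.5) lists no toxicity assessment, so the safeguard is incomplete there, but the documents do not support the general claim.

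It can also be said that pooling *not assessable* with *likely related* may overstate causation just as exclusion may understate it. That is fair, and it is why both columns should be shown. It does not remove the mismatch between 7.5.1 and 8.2.3.3.4.

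**Conclusion.** The point holds for the related-AE table. Followed as written, 8.2.3.3.4 omits a category of events that 7.5.1 leaves within toxicity, so the table may understate related AEs. The direction for counts at a given grade or worse follows from the definitions alone. The size is unknown: zero if no event is rated *not assessable*, and a relative shortfall of 10% to 50% if the assumed share runs from one tenth to one half with one event per patient per item. The all-AE, haematology and biochemistry tables are unaffected. That mixed-cause events make up part of the omitted group is plausible but not established by the documents. The difference in wording within 16.6 is a separate, smaller inconsistency.

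**What to change.** In 8.2.3.3.4, define related AEs as all AEs not rated *unrelated* (likely related plus not assessable), in line with 7.5.1, and show *likely related* alone as a second column. It would help to state how an event with both a treatment cause and a competing cause is to be read in that table. Separately, reconcile the text of 16.6 with its own table, and both with 7.5.1.

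The cost is a sentence or two. Section 7.5.1 already has the rating recorded for every adverse event, so the table needs no new data, even though Appendix M reports that enrolment and treatment are complete. The downside is small: related-AE rates become slightly less favourable, and some events not caused by treatment are included. The second column lets the reader see how much.

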6.2 Before treatment start: randomization step

All pretreatment physical, neurological and quality of life evaluations should be performed within 2 weeks of randomization but after the surgical procedure leading to the diagnosis of anaplastic glioma. All laboratory evaluations must be carried out within 4 weeks from randomization. The initial assessment of disease with MR or CT must be performed between the surgery and the start of radiotherapy, unless patients underwent a biopsy only in which case the pre-operative imaging is sufficient (and only a CT for radiotherapy planning is required). Radiotherapy and concomitant temozolomide should be started within 8 days of randomization.

The baseline evaluations include:

- Complete medical history
- Physical examination including neurological evaluation and vital signs
- Vital signs, blood pressure, height and weight
- WHO-ECOG performance status
- Mini mental status examination (MMSE)
- Quality of Life C30 and BCM20
- Corticosteroid intake
- Complete blood counts: hemoglobin, haematocrit, white blood cells and differential, platelets.
- Serum chemistry: sodium, potassium, calcium, creatinine, urea, glucose, ASAT, ALAT, total bilirubin, alkaline phosphatase, gamma-GT, total protein, LDH.
- Toxicity according to CTCAE v.3
- Gadolinium enhanced MRI or contrast enhanced CT scan of the brain
- Fresh frozen tumor material for translational research (optional)
- Cognitive exam (dedicated centers only)

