10.1 Rationale / objectives and hypothesis (background literature)

Patients with anaplastic glioma can have a poor QoL, but this has not been frequently assessed in large scale studies. It is highly likely that these patients will experience similar symptoms as recently reported in the 26951 and 26981 trials. That is, that patients can suffer from considerable levels of fatigue, have sleep problems, communication deficits, motor dysfunction and leg weakness with impairments in emotional and social functioning and express uncertainty regarding the future and an overall reduced QoL. Therefore, in this study, QoL is an important secondary endpoint. The main objective of QoL assessment within this clinical trial is to determine the impact of no adjuvant chemotherapy versus adjuvant therapy until progression for anaplastic glioma on overall health/QoL. Based on the recent EORTC study 26981, the hypothesis is that we expect no differences between arms using the global QoL scale during treatment, but there may be a later benefit to the adjuvant therapy arm if disease progression is achieved, thereby leading to a better global QoL. Several past neuro-oncological trials have shown an increased progression free survival after more intense initial treatment, without an effect on

overall survival. At present the impact of progression of high-grade glioma on the quality of life is not clear. It is not clear if increasing progression free survival is translated into a longer period with a better preserved quality of life. If that is the case, improvement of progression free survival would become a goal in itself. With this trial we will assess if QOL is decreased at the time of first progression, and if a longer progression free period is translated in a better QOL. To meet these objectives QOL questionnaires will also be administered after the first progression.

A secondary objective is to evaluate the effect of temozolomide on the various symptoms and functioning scales as treatment related side-effects may have a (temporary) negative influence on the health related domains of QoL of these patients. Based on the past study, we may see a slight increase in fatigue and reduction on social functioning in the adjuvant chemotherapy arm. However, once off treatment, we expect to see no differences

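### The adverse-event tables do not use the baseline grades that are collected, so an unchanged pre-treatment symptom cannot be told apart from a new or worsened one

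*Combined protocol and SAP*

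**What the plan says.** Section 6.2 lists "Toxicity according to CTCAE v.3" among the baseline evaluations, and the section 6.6 table marks it mandatory at baseline. Toxicity is graded again weekly during radiotherapy in all arms (section 6.3.1.1), at weeks 4 and 6, four weeks after radiotherapy, before each adjuvant cycle and at the six-monthly assessments.

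Section 8.2.3.3 says: "The safety analyses will be presented overall and by period as defined below". The first of those periods is defined so: "The baseline (BL) period will include all information recorded up to the randomization date".

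The two AE tables follow. For all AEs, section 8.2.3.3.3 reads: "The worst grade of each AE item will be calculated as the maximum grade reported", regardless of seriousness or relationship and over the whole treatment period. Section 8.2.3.3.4 repeats this for events reported "as likely related". Each has a grade 3 or 4 summary. Section 8.2.3.3.4 then rules out formal comparison and p-values, and closes with "Baseline AE grades will not be accounted for in any AE analyses". The plan contains no definition of a treatment-emergent event, no subtraction of baseline and no shift table.

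**The concern.** Patients enter after brain surgery with tumor in place, so some will have headache, fatigue or a motor deficit before the first fraction. Because toxicity is re-graded at every visit, such a symptom is recorded again on treatment and enters the worst-grade table. This holds even on the mildest reading of the closing sentence, namely that records dated before randomization are left out: the on-treatment record of the same symptom stays in.

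The safety of temozolomide, including late effects on cognition, is a secondary objective (section 2.2), and section 1.1.2 names neurotoxicity of combined treatment as a reason for the trial. Neurological and constitutional items are where background from tumor and surgery is most likely. If that background cannot be separated from change on treatment, the tables are least informative on the items of most interest.

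**Working it through.** The plan states no figure for the safety analysis, so there is nothing to reproduce. The check sizes the mechanism under assumed rates.

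**Inputs (all assumed; none is in the documents)**

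- *b*: share of patients whose symptom is present before treatment and recorded again, unchanged or worse, on treatment. It is taken as equal across arms because of randomization.
- *p*: rate of the event in patients without the symptom at baseline (pC without, pT with the treatment in question).
- *r*: rate of worsening in patients already affected (rC, rT).

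**Formulas**

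- Planned all-AE table: rate = b + (1 − b)p; difference = (1 − b)(pT − pC).
- New or worsened: rate = (1 − b)p + br; difference = (1 − b)(pT − pC) + b(rT − rC).
- The planned table therefore loses b(rT − rC) of the absolute difference. If r = p, it shows the fraction (1 − b) of the true difference. If r = 0, it loses nothing in absolute terms.

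**Any grade, pC = 10%, pT = 25%, r = p (true difference 15 points, ratio 2.50)**

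| b | planned rates | difference | ratio |
|---|---|---|---|
| 5% | 14.5% vs 28.75% | 14.25 | 1.98 |
| 10% | 19.0% vs 32.5% | 13.5 | 1.71 |
| 20% | 28.0% vs 40.0% | 12.0 | 1.43 |
| 40% | 46.0% vs 55.0% | 9.0 | 1.20 |

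**Same rates, r = 0, b = 20%.** New or worsened: 0.8 × 10% = 8% vs 0.8 × 25% = 20%, a difference of 12 points and a ratio of 2.50. The planned table gives 28% vs 40%, also 12 points, with a ratio of 1.43. Using baseline restores the ratio here but adds nothing to the absolute difference.

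**Grade 3-4, pC = 2%, pT = 8%, r = p (true difference 6 points, ratio 4.00).** Here *b* is the share already at grade 3-4 before treatment.

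| b | planned rates | difference | ratio |
|---|---|---|---|
| 1% | 2.98% vs 8.92% | 5.94 | 2.99 |
| 2% | 3.96% vs 9.84% | 5.88 | 2.48 |
| 5% | 6.90% vs 12.60% | 5.70 | 1.83 |

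The absolute difference falls by 1% to 5% of its size, while the ratio falls much more.

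**Neutrophils and platelets.** Section 3.2 requires at least 1.5 and 100 × 10⁹/l. With the 5% buffer the floors are 1.5 × 0.95 = 1.425 and 100 × 0.95 = 95. Section 5.5.3.2 places grade 3-4 below 1 and below 50 × 10⁹/l. An eligible patient cannot start there, so *b* is essentially zero for these two items.

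**The case against.** The strongest reply has five parts.

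1. *The plan already has a toxicity filter.* Section 7.5.1 says: "Adverse events not drug related (i.e. reported as unrelated) will not be considered as side effects or toxicity", and the second AE table counts only likely-related events. A stable pre-treatment deficit should not reach that table. This stands, but the filter is partial. It rests on investigator judgement, and no placebo is described. There is also a third category, not assessable. Section 16.4, written for SAEs but with the same categories, reserves likely related for cases where other factors are unlikely or absent. Worsening of an existing deficit could reasonably be coded not assessable and drop out of the related table. In the all-AE table it looks the same as an unchanged deficit of that grade.

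2. *Baseline is not wholly ignored.* A reader might infer that every safety table disregards it and that baseline grades are never shown. The documents do not support that. The sentence governs AE analyses; hematology and biochemistry have their own sections, which merely state no baseline reference. Section 8.2.3.3 defines a baseline period and promises presentation by period, which points to some display of baseline data. How that fits with the closing sentence of 8.2.3.3.4 is left open.

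3. *The size is unknown.* This stands. Section 10.1 says that "patients can suffer from considerable levels of fatigue, have sleep problems, communication deficits, motor dysfunction and leg weakness", but it describes what earlier trials reported on quality of life. It gives no CTCAE prevalence before treatment, and a large background cannot be read from it. The tables also show each worst grade, so a rise into grade 3-4 is visible in aggregate.

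4. *Other endpoints use baseline.* MMSE is analyzed as change (8.2.3.4), neurological deterioration is defined against baseline performance status (7.2), and fatigue is a secondary quality-of-life endpoint. These cover part of the ground, but not the AE items.

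5. *Worst grade without baseline is a prespecified convention, and safety is descriptive.* Both are true, and the radiotherapy-alone arm shows the background rate. But these tables are the only planned AE comparison, so what they can show matters.

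**Conclusion.** The point holds for the AE tables. As planned, the all-AE table, and to a lesser extent the likely-related table, cannot separate a persisting pre-treatment symptom from a new or worsened one. Ratios between arms are pulled towards 1. The absolute difference shrinks relative to the true new-or-worsened difference only if patients already affected worsen at a similar rate; if they do not worsen at all, it is unchanged.

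The effect falls mainly on any-grade neurological and constitutional items. It is small for absolute grade 3-4 differences if severe baseline grades are rare, and negligible for grade 3-4 neutrophils and platelets. Every value of *b*, *p* and *r* above is an assumption, so the direction is secure and the size is not. A common *b* is also a simplification: patients on adjuvant temozolomide are seen every four weeks in addition to the six-monthly visits (section 6.4), so in that phase the distortion need not be pure dilution.

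A reader might go further and infer that the safety conclusions are statistically invalid. They are not: no test, significance level or power calculation depends on these tables. The harm is to interpretation.

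**What to change.** Keep the planned worst-grade tables. Replace the last sentence of section 8.2.3.3.4 with:

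*Beside the worst-grade tables for All AEs and Related AEs, the frequency of AE items whose worst on-treatment grade exceeds the baseline grade (new or worsened) will be tabulated by arm, with a baseline-to-worst-grade shift table.*

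In section 8.2.3.3, say how the baseline period is displayed, so that it agrees with the new sentence. The hematology and biochemistry sections need no change for this point.

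The cost is one derived variable, some extra tables and a stated convention for an item with no baseline grade. The data are already collected, nothing planned is removed, and nothing changes for patients.
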